Quality of life questionnaire- At the preassessment clinic, patients will be asked to fill out a validated quality of life questionnaire (SF-36 health survey).

Intra-operative specimens

Heart muscle biopsies will be obtained at the time of clinically indicated heart surgery. Two small heart samples approximately 0.8 grams each or the size of a cooked rice grain will be taken from the left and right ventricle. The specimens will be preserved in formalin and processed and analysed at the Department of Pathology by a pathologist with a specialist interest in cardiac pathology. The samples will be fixed and analysed with haematoxylin and eosin for structure, Elastin van Gieson stain for elastin, Martius, Scarlet and Blue stain for fibrin, Picrosirius red stain for collagen, Perls' Prussian blue stain for iron, Periodic acid-Schiff stain for polysaccharides, Desmin stain for smooth muscle, CD68 for monocytes, CD45 for leucocytes, smooth muscle actin for smooth muscle and CD31 for vascular endothelium.

[name] 22/12/16 16:42 Deleted: 2 [name] 22/12/16 16:43 Deleted: 1 [name] 22/12/16 16:43 Deleted: 9

By correlating the results of the histological analysis with clinical markers such as left and right ventricle function and pulmonary hypertension, and the cardiac imaging on transthoracic echocardiogram and cardiac MRI this will enable us to grade microscopic changes in the myocardium throughout the spectrum of mitral valve disease from asymptomatic to symptomatic.

In addition, the results of the histological analysis will be the basis of further collaborative work with the Myocardial Function group at the Imperial Centre for Translational and Experimental Medicine.

Post-operative follow up

6-8 weeks- it is normal practice for patients to be reviewed at 6-8 weeks after surgery in clinic with clinical history and examination. Patients will be asked to fill in a quality of life questionnaire at this time.

6-9 months- Patients will have a repeat transthoracic echocardiogram, cardiac MRI, CPET, pulmonary function tests. A quality of life questionnaire will be mailed to patients with a self-addressed envelope.

12 months- it is normal practice for patients to be followed up at 12 months after surgery with clinical history and examination.

Review of investigations

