3.1 STUDY OUTCOME MEASURES

- 1. The accuracy of transthoracic echocardiogram compared to right heart catheterization in measuring pulmonary artery pressures in a prospective severe mitral valve disease cohort.
- Correlation between objective measurements of exercise capacity on cardiopulmonary exercise testing with quality of life and measurement of cardiac function on transthoracic echocardiogram and cardiac MRI in severe mitral valve disease.
- 3. Histological changes in the left and right ventricle in severe mitral valve disease.
- Pilot data on changes in exercise capacity and quality of life and relationship to transthoracic echocardiogram, cardiac MRI and pulmonary function tests early after mitral valve surgery.

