6. ASSESSMENT AND FOLLOW-UP

Patients will be followed up at 6-8 weeks after surgery in clinic as normal practice and will be asked to fill in a quality of life questionnaire at this time.

It is normal practice for patients to be followed up at one year after surgery with a repeat transthoracic echocardiogram prior to this appointment. Before this appointment, they will have an additional repeat cardiac MRI, CPET, pulmonary function tests and quality of life questionnaire at 6-9 months after surgery.

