this outcome we have run univariable and multivariable logistic regression model. In consideration of the fact that the overall number of events for this outcome was limited, the final multiple model was a parsimonious model developed using a meaningful selection of the variables that were considered relevant in previous published research (preoperative LVEF \leq 60 %, LVESD \geq 40 mm and ppVO2 % $\leq 84\%$) plus the class of surgical indication.

Correlation between TTE parameters and MRI parameters

Linear models have been run to compare some TTE parameters with the same MRI models.

Comparing changes in quality of life between class of indication of surgery Linear mixed effects models were fitted for longitudinal (repeated measures) outcomes (physical functioning and social functioning) adjusted for time, preoperative percentage predicted peak VO2, preoperative LVEDD and preoperative LVESD.

For each of the main outcomes a stepwise approach has been used to model the data: first, an unconditional means model was run to describe the data and to test the null hypothesis; then an Unconditional Growth Model to set up the slope has been run followed by a Conditional Growth model (to set up the intercept). The unconditional mean model determines if the intercept is different from zero and if there is subjectrelated variability. The unconditional growth model can have a fixed or a random slope: the fixed slope is based on the assumption that each individual in the dataset is following a similar pattern over time, while the random slope allows individual variability. Both models have been run to find out the best fitting model. The Conditional growth model is the final step and it is the complete final model adjusted for the covariates. All models were fitted using maximum likelihood methods.

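### A single slope for quality of life across three visits that span surgery misstates the 6-8 week change unless that visit happens to lie on the line between the other two

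*SAP*

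**What the plan says.** In the SAP, under the heading on changes in quality of life by class of indication, linear mixed models are fitted to physical and social functioning, "adjusted for time, preoperative percentage predicted peak VO2, preoperative LVEDD and preoperative LVESD". The models are built in steps. After an unconditional means model, "then an Unconditional Growth Model to set up the slope has been run followed by a Conditional Growth model". The only choice described for time concerns variation between patients: "The unconditional growth model can have a fixed or a random slope". No quadratic, piecewise or categorical time term is mentioned, no check of linearity is planned, and the unit or coding of time is not given.

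The protocol sets three quality-of-life assessments:

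- before surgery, at the preassessment clinic (section 3);
- early after surgery: "Patients will be followed up at 6-8 weeks after surgery in clinic as normal practice", with a questionnaire at that visit (section 6; month 2 in the Appendix 1 table);
- later: "pulmonary function tests and quality of life questionnaire at 6-9 months after surgery" (section 6).

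Appendix 1 shows none at 12 months. The fourth outcome measure in section 3.1 begins "Pilot data on changes in exercise capacity and quality of life" and refers to the period early after mitral valve surgery.

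**The concern.** Open-heart surgery falls between the first and second questionnaires. A straight mean line over the three visits assumes that the change by 6-8 weeks is a fixed fraction of the change by 6-9 months. The SAP neither states nor tests this.

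Comparing a fixed with a random slope does not test it. The SAP says "the fixed slope is based on the assumption that each individual in the dataset is following a similar pattern over time". A random slope relaxes that by letting patients' own lines differ, but the mean stays straight. The pre-operative covariates do not bend it either, because they do not change over time. A better fit for one of these models therefore says nothing about the shape of the average course.

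At stake is whether the analysis can report what happened at the 6-8 week visit, how far the 6-9 month change is distorted by that visit, and whether a difference between classes in the shape of recovery could be seen.

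**Working it through.** The documents give no expected scores, standard deviations or sample size calculation for quality of life, so there is no figure to reproduce. The mean scores below are assumptions chosen to show a range.

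**Visit times.** Pre-operative visit: t = 0. Second visit: the midpoint of 6-8 weeks is 7 weeks, and 7 x 7 / 30.4375 = 1.61, taken as 1.6 months. Third visit: the midpoint of 6-9 months is 7.5 months.

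**Slope.** With complete data at common visit times, the mean slope of either mixed model equals the least-squares slope through the three visit means. The mean time is 9.1 / 3 = 3.033. The deviations are -3.033, -1.433 and +4.467, with sum of squares 9.201 + 2.054 + 19.951 = 31.207. Each weight is deviation / 31.207: **-0.097, -0.046 and +0.143** per month. The middle weight is negative, so a lower 6-8 week score makes the fitted line rise faster.

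Write d2 and d3 for the true changes from baseline at the second and third visits:

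- slope = -0.0459 d2 + 0.1431 d3
- fitted change at 6-8 weeks = 1.6 x slope
- fitted change at 6-9 months = 7.5 x slope

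**Time in months, d3 = +15.** The straight line passes through 15 x 1.6 / 7.5 = +3.2 at the second visit.

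| True d2 | Slope | Fitted 6-8 weeks (error) | Fitted 6-9 months (error) |
|---|---|---|---|
| -10 | 2.606 | +4.2 (+14.2) | +19.5 (+4.5) |
| 0 | 2.147 | +3.4 (+3.4) | +16.1 (+1.1) |
| +3.2 | 2.000 | +3.2 (0) | +15.0 (0) |
| +10 | 1.688 | +2.7 (-7.3) | +12.7 (-2.3) |

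The row at +3.2 is the check: on the line there is no error. In general, with departure = d2 - (1.6/7.5) d3, the 6-8 week error is -(1 + 1.6 x 0.0459) = -1.07 times the departure, and the 6-9 month error is -(7.5 x 0.0459) = -0.34 times the departure.

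**Other times within the windows**, for -10 and +15: visits at 1.38 and 6 months give +4.5 and +19.4; 1.84 and 9 months give +4.0 and +19.6; 2 and 7.5 months give +5.1 and +19.1.

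**Visits coded 0, 1, 2.** The weights are -0.5, 0 and +0.5, so the slope is 7.5 whatever d2 is. The fitted 6-9 month change is +15, which is correct. The fitted 6-8 week change is always +7.5, an error of +17.5, +7.5 or -2.5 for d2 of -10, 0 or +10.

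**Simulation.** 200 data sets of 50 patients, true changes -10 and +15, assumed between-patient SD 18 and residual SD 14, maximum likelihood. Linear time averaged +4.1 and +19.3; categorical visit gave -9.9 and +14.8. A likelihood-ratio test of linear against categorical time rejected linearity in all 200. A departure of that size would be found if someone looked.

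**Class comparison, time in months.** If the departure is the same in both classes, it cancels from the difference between classes. Suppose instead that both classes gain 15 by the last visit, but one has d2 = -10 and the other d2 = +3.2. The fitted 6-9 month changes are 19.5 and 15.0, a difference of 4.5 where the truth is 0. The fitted 6-8 week changes are 4.2 and 3.2, a difference of +1.0 where the truth is -13.2.

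**The case against.** Four points can fairly be made against this.

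1. **No dip is documented.** A reader might infer that patients are known to be worse at 6-8 weeks and that the model will report the opposite. The documents do not support that. They describe the visit as a routine clinic review and give no expected course. The point rests only on the 6-8 week mean not being on the line; the table covers a fall, no change and an early gain.
2. **The 6-9 month error depends on coding.** A reader might infer that both changes are wrong whatever the coding. With visits coded 0, 1, 2, the last-visit change is right. This stands. The 6-8 week error remains under both codings.
3. **The section compares classes.** A reader might infer that this comparison is invalid. It is not, if both classes depart equally from their lines. This stands as a limit.
4. **No separate 6-8 week contrast is requested.** Post-operative exercise testing, MRI and lung function are all at 6-9 months, so the early period in the fourth outcome measure must include that visit. It is also a pilot outcome, outside the primary and secondary objectives in protocol section 2. This limits the weight of the point. Still, a questionnaire is collected at 6-8 weeks, and a single slope cannot report what it shows.

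**Conclusion.** The concern holds in limited form. The SAP imposes a straight mean course across an operation, and its comparison of fixed with random slopes cannot reveal a departure.

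- **6-8 week change:** misstated under either coding unless the mean lies on the line. The error is about 3 to 14 points with time in months, for the assumed departures and a +15 gain at the last visit.
- **6-9 month change:** misstated by about -2 to +4.5 points with time in months; unbiased with visits coded 0, 1, 2.
- **Class comparison:** biased only if the shape of recovery differs by class, which this model cannot show.

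These sizes rest on assumed mean scores, complete data, visits at common times and the pre-operative questionnaire taken as time zero. The direction of any real error is unknown.

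A separate gap bears on the remedy: the listed adjustment terms include neither class nor class by time, although the section heading implies that class is the comparison of interest.

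**What to change.** In the quality-of-life section of the SAP:

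- Replace the linear slope with visit as a three-level factor: pre-operative, 6-8 weeks, 6-9 months.
- Include class of indication and class-by-visit terms, keeping the listed pre-operative covariates.
- Report change from pre-operative at 6-8 weeks and at 6-9 months, overall and by class, with confidence intervals.
- Model within-patient correlation with an unstructured covariance over the three visits, and a random intercept as the stated fallback if that does not converge. A random intercept alone is not the first choice, because it assumes equal variance and equal correlation across unequally spaced visits on either side of surgery.

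**Cost.** No new data are needed. With two classes there are six visit-by-class means instead of two intercepts and two slopes, so two more fixed parameters. The covariance has six parameters (three variances, three covariances) instead of four for a random intercept and slope with residual. In about 50 patients, intervals will be slightly wider. The SAP describes the models as already run, so both need refitting and re-reporting.
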